5.5 Statistical models

5.5.1 **Primary analysis**

The null hypothesis for the primary analysis is the ratio of the geometric means of NT-proBNP for the sacubitril/valsartan and enalapril group are equal. An ANCOVA model will be used. The model will have the time-averaged proportional change from baseline in a logarithmic scale be the dependent variable with treatment as a fixed effect factor and the logarithmic baseline value as a covariate. The general form for the ANCOVA model is:

$$y_{ij} = \mu + T_i + B(x_{ij} - \overline{x_i}) + E_{ij}$$

PROC MIXED in SAS will be used for the analysis. The LSMEANS option will be used with options of CL to output the confidence limits.

5.5.2 Key secondary analysis

Similar to the primary analysis, the null hypothesis for the secondary analysis is the ratio of the geometric means of different biomarkers (BNP to NT-proBNP ratio, hs-Troponin and urinary cGMP) for the sacubitril/valsartan and enalapril group are equal. An ANCOVA model will be used. The model will have the time-averaged proportional change from baseline in a logarithmic scale be the dependent variable with treatment as a fixed effect factor and the logarithmic baseline value as a covariate. The general form for the ANCOVA model is:

$$y_{ij} = \mu + T_i + B(x_{ij} - \overline{x_i}) + E_{ij}$$

PROC MIXED in SAS will be used for the analysis. The LSMEANS option will be used with options of CL to output the confidence limits.

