8.5 Adjudication Committee

It is important that the investigator pays special attention to any swelling or edema that may resemble angioedema or angioedema-like events that may be reported by patients. There will be a separate eCRF for angioedema events. If such an event occurs, the investigator will complete an Adjudication Questionnaire for an Angioedema-like Event form (provided by Novartis) to summarize the event, its treatment, and its ultimate outcome and communicate this report to Novartis as soon as possible. Follow-up reports must be communicated to Novartis as soon as new information regarding the event becomes available. All hospital records related to the event must be communicated to Novartis.

Occasionally, the investigator may be contacted by the Novartis regarding AEs that were reported on behalf of patients that may resemble an angioedema -like event. The investigator or his/her delegated staff must complete the required report forms and supply the required medical records for such events, regardless of whether the investigator views the event in question as angioedema or not.

All angioedema reports will be forwarded to an angioedema adjudication committee by Novartis for assessment.

Submission of an angioedema report is not a substitution for the submission of a SA E report. If an angioedema-like event satisfies the definition of a SAE, the investigator must submit a SAE report in addition to the Adjudication Questionnaire for an Angioedema-like Event.

9 Data analysis

A designated Contract Research Organization will perform the statistical analysis.

It is planned that the data from all centers that participate in this protocol will be combined, so that an adequate number of subjects will be available for analysis.

Unless otherwise specified, all statistical tests will be conducted against a two-sided alternative hypothesis, employing a significance level of 0.05.

Efficacy, safety, and other data will be summarized. For continuous variables, summary statistics (mean, standard deviation, median, 25th and 75th percentiles, interquartile range, minimum, and maximum) at each time point and for change from baseline to each time point will be reported by treatment group.

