9.5.3 Other safety variables

The safety and tolerability assessments are listed below:

- AEs and SAEs
- Sitting systolic, diastolic BP, and pulse pressure
- Heart rate
- Laboratory values

The assessment of safety will be based primarily on the frequency of adverse events, SAEs, and laboratory abnormalities. Other safety data will be summarized as appropriate.

The incidence of treatment-emergent adverse events (new or worsened) will be summarized by primary system organ class, preferred term, severity, and relationship to study drug. In addition, the incidence of death, SAEs, and AEs leading to discontinuation will be summarized separately by primary system organ class and preferred term.

Laboratory data will be summarized by presenting shift tables using extended reference ranges (baseline to most extreme post-baseline value), by presenting summary statistics of raw data and change from baseline values (mean, median, standard deviation, 25th and 75th percentiles, interquartile range, minimum and maximum) and by the flagging of notable values in data listings.

Data from other tests (e.g., ECG or vital signs) will be listed, notable values will be flagged, and any other information collected will be listed as appropriate.

Safety analyses will be performed based on the Safety Set. There will be no inferential analyses of the safety data.

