9.7 Sample size calculation

Assuming a significance level of 0.05 and 85% power, a sample size of 882 patients would be needed to detect an 18% reduction in the geometric mean of the time-averaged proportional change from baseline (average of Weeks 4 and 8) in NT-proBNP for the sacubitril/valsartan treatment group assuming a value of 0.95 for the enalapril group, a common standard deviation of 0.85 and a 25% rate of missing/non-evaluable samples. The estimates are based on the day 5 to day 14 data from the RELAX -AHF study. The standard deviation estimate is supported by data from PARADIGM.

The assumption of a 18% reduction in the geometric mean for NT-proBNP for the sacubitril/valsartan treatment group vs. the enalapril group is consistent with NT-proBNP results seen in PARADIGM (26% and 25% relative reduction of sacubitril/valsartan vs. enalapril at Week 4 and Month 8 respectively), PARAMOUNT (23% relative of sacubitril/valsartan vs. valsartan at Week 12) and RELAX-AHF (19% relative reduction of serelaxin vs. placebo at Day 2).

		0	10 1			
Change in GM for enalapril	Common SD	Relative reduction in GM for sacubitril/valsartan group compared to enalapril group	Change in GM for sacubitril/valsartan group	Power	Non- evaluable rate	Total sample size after adjusting for non- evaluable rate
.95	.85	15%	.81	85%	10%	1096
.95	.85	15%	.81	90%	10%	1280
.95	.85	18%	.78	85%	10%	736
.95	.85	18%	.78	90%	10%	860
.95	.85	18%	.78	85%	25%	882
.95	.85	20%	.76	85%	10%	582
.95	.85	20%	.76	90%	10%	680

Table 9-1Sample size and power for various rate of reduction in
sacubitril/valsartan group given alpha =0.05:

10 Ethical considerations

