2.1 Data analysis general information

, a Novartis-designated Contract Research Organization (CRO) will be performing all analyses outlined in this SAP. SAS[®] version 9.3 (or higher) will be used for all analyses.

Data from all centers that participate in this protocol will be combined, so that an adequate number of patients will be available for analysis.

Unless otherwise specified, for continuous data, the mean, standard deviation, median, first and third quartile, interquartile range, and minimum and maximum values will be presented. For categorical data, frequencies and percentages will be presented. All statistical tests will be conducted against a two-sided alternative hypothesis, employing a significance level of 0.05.

All data will be provided in listings in addition to summaries described below.

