2.6 Analysis of the key secondary objective

No key secondary objective.

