2.7.1 Secondary endpoints

Secondary endpoints include the following:

- The proportional change in NT-proBNP from baseline to Week 8
- Incidence of symptomatic hypotension during 8 weeks of treatment
- Incidence of hyperkalemia (potassium >5.5 mEq/L) during 8 weeks of treatment
- Incidence of angioedema during 8 weeks of treatment
- Biomarkers: hs-Troponin T (high sensitivity), urinary cGMP (UcGMP), UcGMP to urinary creatinine ratio, BNP, NT-proBNP to BNP ratio, and BNP to NT-proBNP ratio at 4 and 8 weeks

Novartis

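### Secondary biomarkers: null hypotheses are stated at the full two-sided 0.05 with no order, gate on the primary or nominal-only status, and the SAP contradicts itself on whether a key secondary analysis exists

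*SAP*

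**What the plan says.** - **Level.** SAP 2.1: "All statistical tests will be conducted against a two-sided alternative hypothesis, employing a significance level of 0.05". The opening of protocol section 9 gives the same level, with an exception only where something else is specified: "Unless otherwise specified, all statistical tests will be conducted against a two-sided alternative hypothesis, employing a significance level of 0.05".
- **Key secondary.** SAP 2.6 states "No key secondary objective". Appendix 5.5.2 nevertheless carries a key-secondary heading and writes that "the null hypothesis for the secondary analysis is the ratio of the geometric means of different biomarkers" (BNP to NT-proBNP ratio, hs-Troponin, urinary cGMP) being equal in the two groups. Week 8 NT-proBNP, the secondary endpoint added by protocol Amendment 2, is not mentioned there.
- **The list.** SAP 2.7.1 has Week 8 NT-proBNP, three safety incidences and six biomarker measures. The biomarkers are hs-Troponin T, urinary cGMP and "UcGMP to urinary creatinine ratio, BNP, NT-proBNP to BNP ratio, and BNP to NT-proBNP ratio at 4 and 8 weeks". SAP section 4 declares three of the six as additions to the protocol.
- **The output.** SAP 2.7.2 gives each NT-proBNP and biomarker endpoint an ANCOVA, with a ratio of geometric means and a 95% confidence interval. Most biomarkers also get separate analyses at Weeks 1, 2, 4 and 8. The safety secondaries get a relative risk (protocol 9.5.1, SAP 2.7.2), and protocol 9.5.3 says: "There will be no inferential analyses of the safety data".
- **What is absent.** Neither protocol 9.5.1 nor SAP 2.7 contains a testing order, a condition on the primary result, an alpha split, or a statement that the intervals are unadjusted. The heading of protocol 9.5 mentions exploratory variables, but no secondary endpoint is called exploratory.

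**The concern.** Written null hypotheses together with a blanket 0.05 are a testing plan. A plan that tests several secondary endpoints should say which results can support a claim and on what condition. This one does not. A biomarker interval that excludes 1 could be presented as a significant pre-specified secondary finding even if the primary comparison fails, and nothing in the SAP would stop it.

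The conflict between 2.6 and 5.5.2 makes this worse. One section says that no secondary objective is singled out. The other singles out three biomarkers and leaves out the secondary endpoint closest to the primary. The reader cannot tell which secondary results carry inferential weight.

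**Working it through.** **1. Where the 0.05 is spent.** The only power statement is for the primary: "Assuming a significance level of 0.05 and 85% power, a sample size of 882 patients would be needed". The inputs in protocol 9.7 are an 18% reduction, SD 0.85 (taken as log scale), 25% non-evaluable and 1:1 allocation.

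- δ = −ln(0.82) = 0.198
- n per arm = 2 × (1.960 + 1.036)² × 0.85² / 0.198² = 329.4, rounded up to 330
- 330 / 0.75 = 440 per arm, 880 in total, against 882 stated
- A t-based version gives 331 per arm, and 662 / 0.75 = 883

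The plan's figure is reproduced. It uses the full 0.05 on one endpoint and one contrast, so the primary needs no adjustment. The plan gives no familywise figure for the secondaries.

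**2. Counting the secondary tests** (one main analysis per endpoint).

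- k = 3: the biomarkers with a written null (SAP 5.5.2).
- k = 4: these plus Week 8 NT-proBNP.
- k = 6: Week 8 NT-proBNP plus the six biomarkers in SAP 2.7.1 makes seven. BNP to NT-proBNP and NT-proBNP to BNP are counted as one, which leaves six.

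**3. Chance of at least one false positive, all nulls true, independent tests.** Formula: 1 − 0.95^k.

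| k | Calculation | Result |
|---|---|---|
| 3 | 1 − 0.8574 | 14.3% |
| 4 | 1 − 0.8145 | 18.5% |
| 6 | 1 − 0.7351 | 26.5% |

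**4. Effect of correlation.** The documents give none, so these are assumptions. For equicorrelated normal test statistics, each tested two-sided at 0.05:

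| k | Correlation 0 | 0.5 | 0.9 |
|---|---|---|---|
| 4 | 18.5% | 16% | 9% |
| 6 | 26.5% | 21% | 11% |

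A common correlation across troponin, urinary cGMP and the peptides is a crude assumption. A structured simulation was also run for the six endpoints. It set BNP with NT-proBNP, and urinary cGMP with its creatinine ratio, at correlations of 0.5 to 0.9, gave troponin a correlation of 0.2 to 0.3 with the peptides, and derived the peptide ratio from the two peptides. It gave 24.1% falling to 21.5%.

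**5. If the expected peptide effects are real.** Protocol 1.1 reports NT-proBNP 25% lower and BNP about 23% higher than on enalapril in the earlier chronic heart failure trial. If that carries over, the nulls for Week 8 NT-proBNP, BNP and their ratio are false and cannot give false positives.

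- Of the six, three remain (troponin, urinary cGMP, cGMP to creatinine): at most about 1 − 0.95³ = 14.3%, and less because the two cGMP measures are related.
- Of the four, two remain (troponin, urinary cGMP): 1 − 0.95² = 9.75% if independent.

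**6. What is not counted.** SAP 2.7.2 also has by-visit analyses: five measures × four visits, plus hs-Troponin T × three visits, makes 23. Reading these as tests would raise the figures.

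**The case against.** The strongest reply is that the planned secondary output is estimation. SAP 2.7.2 asks for ratios with 95% intervals, and 5.5.2 asks only for least-squares means with confidence limits. No secondary analysis requests a p-value, whereas the responder analysis in SAP 2.5.4 does. The 0.05 sentence governs tests that are performed and does not turn every interval into a test. The 5.5.2 heading may also be a leftover, since its text speaks only of the secondary analysis and its three biomarkers match the protocol's list.

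Much of this stands, and it limits the point:

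- A reader might infer that every secondary endpoint has a stated null and is tested at 0.05. Only three biomarkers have a written null. Week 8 NT-proBNP, BNP, the cGMP to creatinine ratio and the NT-proBNP to BNP ratio have models and intervals only.
- A reader might add the three safety relative risks and count nine tests. Protocol 9.5.3 rules out safety inference, so those intervals read as descriptive.
- A reader might treat the two BNP/NT-proBNP ratios as exact mirror images. That is true by visit on the log scale. In the time-averaged analysis the values are averaged before taking logs, so the two can differ slightly if that average is arithmetic. Counting them as one is a simplification that lowers k.

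The reply does not remove the core. A written null hypothesis is testing language, no sentence gives the secondary intervals nominal status, and 2.6 and 5.5.2 cannot both be right. Parts of the public documents are blacked out, but the secondary analysis sections show no visible gap where a multiplicity rule would be expected.

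**Conclusion.** The point holds for the secondary biomarkers and Week 8 NT-proBNP: null hypotheses for three biomarkers at an unadjusted 0.05, no order, gate or nominal-only statement, and an internal contradiction about key secondary status. It does not touch the primary endpoint, whose type I error stays at 0.05.

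The size is best given as a range. With all nulls true and independent tests it is 14% (three stated nulls), 18.5% (with Week 8 NT-proBNP) or 26.5% (six distinct endpoints). For the six it drops to about 21% at a common correlation of 0.5 and 11% at 0.9. The figures for four and six go beyond the written nulls, because they treat a 95% interval that excludes 1 as a significant result. It would be tempting to quote 21% alone, but that needs both six tests and a correlation that the documents do not state. All figures fall if the expected effects on BNP and NT-proBNP are real. Every scenario tabulated or derived above still exceeds 5%. The missing claim rule matters whichever figure applies.

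**What to change.** In SAP 2.7.2, state that Week 8 NT-proBNP is tested at two-sided 0.05 only if the primary is significant. This fixed sequence keeps the chance of any false claim across those two endpoints at no more than 0.05. State also that all other secondary biomarker analyses are reported as estimates with nominal, unadjusted 95% confidence intervals and no claim of significance. Retitle 5.5.2 *Secondary biomarker analyses* and remove its testing language, so that it agrees with 2.6.

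The cost is SAP wording before database lock, with no new data or patients and no alpha taken from the primary. The downside is that biomarker results can no longer be called statistically significant secondary findings.

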5.6 Rule of exclusion criteria of analysis sets

Table 1 Protocol deviations that cause subjects to be excluded **Deviation Description of Deviation Exclusion in Analyses** ID D01 Patient met one or more of the Exclusion from PPS Discontinuation of Study Drug criteria but study drug was not discontinued E02 Patient is enrolled in another clinical **Exclusion from PPS** trial involving an investigational agent or investigational device E03 Patients has а **Exclusion from PPS** history of hypersensitivity, known or suspected contraindications, or intolerance to the study drugs, including ACEIs, ARBs, or Sacubitril (NEP inhibitor) **Exclusion from PPS** E04 Patient has a history of angioedema related to previous ACE inhibitor or ARB therapy E11 The patient had implantation of a **Exclusion from PPS** cardiac resynchronization therapy device (CRTD) within the prior 3 months from Visit 1, the patient intends to have implantation of a cardiac resynchronization therapy device (CRTD) E19 Patient is a pregnant or nursing **Exclusion from PPS** (lactating) women, where pregnancy is defined as the state of a female after conception and until the termination of gestation, confirmed by a positive hCG laboratory test LVEF was not < 40% within the past Exclusion from PPS I07 6 months (including current hospitalization) using echocardiography, multi gated acquisition scan (MUGA), CT scanning 109 Patient did not have an elevated NT-**Exclusion from PPS** proBNP \geq 1600pg/mL or BNP \geq 400 pg/mL during current hospitalization

Deviation ID	Description of Deviation	Exclusion in Analyses
M01	Patient had concomitant intake of a prohibited medication as outlined in the protocol	Exclusion from PPS
O04	Patient randomized in error and not dosed with study drug	Exclusion from FAS and PPS
O05	Missing NT-ProBNP sample at either baseline, week 4 or week 8	Exclusion from PPS
O06	Patient took first dose of study drug before baseline NT-proBNP sample was drawn	Exclusion from PPS
007	Patient missed 1 or more consecutive dose(s) of study drug immediately or prior to visit 5 or visit 7	Exclusion from PPS

Table 2Patient Classification

Analysis Set	PD ID that cause subjects to be excluded	Non-PD criteria that cause subjects to be excluded
RS	NA	Not randomized
FAS	O04	Not in RS
PPS	D01, E02, E03, E04, E11, E19, I07, I09, M01, O04, O05, O06, O07	Not in FAS
SS	NA	No double-blind study treatment received

6 Reference
